3.1 Study procedures objectives and outcomes

	Objectives	Outcome Measures	Timepoint(s)
Primary	1) Examine and compare the prevalence of ILD in patients with varying severity of COVID-19. (Non-hospitalised will be compared with hospitalised patients and COVID severity defined as varying levels of respiratory support)	MDT diagnosis of ILD at 12 months (+/- 3 months) after acute infection	12 months (+/- 3 months) post SARS-CoV-2 NB: Need 2 time points, 6 months apart, between 3 and 15 months post-acute SARS-CoV-2
Secondary	Determine progressive lung function impairment between 3 and 12 months	Lung function decline: ≥10% relative decline in FVC or DLco OR Imaging deterioration: increasing radiological extent of PC-ILD using image analysis or MDT discussion	Need 2 time points, 6 months apart, between 3 and 15 months post-acute SARS-CoV-2
	Resolution of ILD	Any of the following: ≥10% relative improvement in FVC, DLco, or reduction of radiological extent.	12 months (+/- 3 months) post SARS-CoV-2 Need 2 time points, 6 months apart, between 3 and 15 months post-acute SARS-CoV-2
	Persistence of ILD in those not meeting definition of progression or resolution		12 months (+/- 3 months) post SARS-CoV-2 2 time points, 6 months apart, between 3 and 15 months post-acute SARS-CoV-2
	Persistence of ILAs		12 months (+/- 3 months) post SARS-CoV-2

			Need 2 time points, 6 months apart, between 3 and 15 months post-acute SARS-CoV-2
	In hospitalised patients only: Assess the relationship between initial severity of acute infection and ILD	Markers of severity of acute infection (e.g. CRP)	12 months (+/- 3 months) post SARS-CoV-2 Need 2 time points, 6 months apart, between 3 and 15 months post-acute SARS-CoV-2
	In hospitalised patients only Assess the impact of specific medical therapy used in the acute setting and ILD e.g. antivirals, immunomodulation	Medical therapy used for acute infection	12 months (+/- 3 months) post SARS-CoV-2 Need 2 time points, 6 months apart, between 3 and 15 months post-acute SARS-CoV-2
	Evaluate breathlessness, fatigue and cognition	Medical research council dyspnoea scale Dyspnoea 12 FACIT-F Montreal Cognition Assessment (MOCA)	3 month, 6 months (+/- 6 weeks) and 12 months (+/- 3 months) post SARS-CoV-2 infection
	Evaluate the quality of life of patients with COVID-19	Short Form-36 (SF-36) EQ5D-5L	3 month, 6 months (+/- 6 weeks) and 12 months (+/- 3 months) post SARS-CoV-2 infection

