	Assess impact of COVID19 on aerobic capacity and endurance.	Incremental shuttle walk test or cardiopulmonary exercise test, if clinically indicated	3 month, 6 months (+/- 6 weeks) and 12 months (+/- 3 months) post SARS-CoV-2 infection
Exploratory	Exploratory circulating biomarkers will be correlated with ILA/ILD	whole blood RNA sequencing (including peripheral blood mononuclear cells) and analysis of epigenetic modifications and proteomics	3 month, 6 months (+/- 6 weeks) and 12 months (+/- 3 months) post SARS-CoV-2 infection
	Compare serological and cellular measures of epithelial and endothelial injury and thrombosis	Serum biomarkers of epithelial and endothelial injury, NETosis and thrombosis Cellular measurements in these same patients. Serum/ Plasma: Nordic biomarkers, LRG-1, MMP-7 etc; NETs	3 month, 6 months (+/- 6 weeks) and 12 months (+/- 3 months) post SARS-CoV-2 infection
	Compare genetic risk factors for lung fibrosis and radiological progression, continuously and dichotomised	genome-wide array genotyping Genetic testing from blood/ saliva of putative candidate genes and use of GENOMIC data, and telomere length in a subset	No sooner than 3 month visit
	Assess the relationship between routinely collected laboratory parameters markers	Laboratory parameters (including CRP, FBC) and extent of ILD in patients	3 month, 6 months (+/- 6 weeks) and 12 months (+/- 3 months) post SARS-CoV-2 infection

3.2 Description of study procedure(s) Tier 1 and Tier 2

Initial patient approach

Eligibility assessment by clinical team

Study information and invitation letter provided to eligible patients for data only, Tier 1 participation.

Description of study procedure(s) Tier 2

History and Examination (10 mins) : Medical history, allergies, medications and anthropometric measurements including height, weight, and body mass index will be recorded during the study visit (or taken from the hospital notes. Or PHOPS data)

Blood sample collection (10 mins) :

Samples will be taken for plasma/ serum for epithelial and endothelial damage biomarkers, coagulation and genetics

Questionnaires (45 mins)

Participants will be provided with seven questionnaires; 36 Short-Form Survey (SF-36), Clinical Frailty Scale (CFS), Patient Health Questionnaire 9 (PHQ9), Montreal Cognition Assessment (MOCA), Dyspnoea-12 score, EQ5D-5L, FACIT-F at the end of each study visit.

There are no investigations required for participants co-enrolled in the PHOSP-COVID study.

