3.2.1 Baseline and follow up assessments

Initial patient approach

Eligibility assessment by clinical team

Study information and invitation letter provided to eligible patients

Visit 1 (~3 months) (Post COVID-19 infection patients)

1. Review of eligibility with participant
2. Obtain written informed consent
3. History and anthropometric measurements, e.g. height, weight, body mass index (BMI)
4. Blood sample (6-10 ml) collection
5. Pulmonary function test (20 minutes)
6. *Optional* 6-minute walk test (6MWT) (10 minutes)
7. Quality of Life questionnaire (SF-36) (10 minutes)
8. Clinical Frailty Scale (CFS) (5 minutes)
9. Personal health questionnaire (PHQ) (10 minutes)
10. Montreal Cognitive Assessment MOCA (10 minutes)
11. Dyspnea 12 score (10 minutes)
12. EQ5D-5L (10 minutes)
13. FACIT-F questionnaire (10 minutes)

Optional Visit 2 (~6 months) (Post COVID-19 infection patients and matched controls)

All visit 1 assessments will be repeated.

Visit 3 (~12 months) (Post COVID-19 infection patients)

All visit 1 assessments will be repeated.

Visits will be scheduled to take place over 1 day.

Visit 2 is optional,

Visits 1 and 3 are obligatory.

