5.0 ASSESMENT AND FOLLOW UP

5.1 Optional follow up and assessment

As previously detailed in section 3.3 above, Tier 2 participants may also agree to a final follow up assessment and an optional interim assessment

Optional Visit 2 (~6 months) (Post COVID-19 infection patients and matched controls)

All visit 1 assessments will be repeated. All visit 1 assessments will be repeated.

Visits will be scheduled to take place over 1 day. Visit 2 is optional, visits 1 and 3 are obligatory. For research specific visits, participants will be offered reimbursement for travel expenses. This includes reimbursement for petrol, car parking, taxis.

Clinical outcome data and images from clinical scans for all COVID-19 patients will also be collected from around the time of infection and hospitalisation and follow up. Laboratory analyses and chest imaging results undertaken for clinical reasons will also be collected. Access to participant medical records and any relevant hospital data that is recorded as part of routine standard of care; i.e., CT-Scans, blood results and disease progression data etc. will be obtained with patient consent from hospital electronic patient records and NHS digital. The end of the study will be the point at which the final patient follow-up and assessment have been completed.

A detailed Image Management protocol for the UKILD-Post COVID Study provides a comprehensive outline of the purpose, operation, methods, policies, and governance of Image collection for UKILD. It describes the procedures used to collect and store images. (appendix 1)

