6.4 Serious AEs

An SAE form should be completed and emailed to the Chief Investigator within 24 hours. However, relapse and death due to COVID -19, and hospitalisations for elective treatment of a pre-existing condition do not need reporting as SAEs.

All SAEs should be reported to the London Riverside REC where in the opinion of the Chief Investigator, the event was:

- 'related', ie resulted from the administration of any of the research procedures; and
- 'unexpected', ie an event that is not listed in the protocol as an expected occurrence

Reports of related and unexpected SAEs should be submitted within 15 days of the Chief Investigator becoming aware of the event, using the NRES SAE form for non-IMP studies. The Chief Investigator must also notify the Sponsor of all related and unexpected SAEs.

Local investigators should report any SAEs as required by their Local Research Ethics Committee, Sponsor and/or Research & Development Office.

Contact details for reporting [contact]**CI email (and contact details below)****Fax: N/A, attention [name]****Please send SAE forms to: [contact]****[contact] (Mon to Fri 09.00 – 17.00)****7.0 STATISTICS AND DATA ANALYSIS**

The prevalence of MDT-confirmed PC-ILD at both early (up to 6 months) and again at late (10-15 month) time-points and will be assessed within the total study population. The prevalence of broader radiological abnormalities and phenotypic patterns will also be assessed in a descriptive analysis, together with demographics, haematological and biochemical profiles, physiological performance, and patient-reported outcome measures. Analyses will be performed overall and stratified according to hospitalised and non-hospitalised, as well as severity of infection in hospitalised patients defined above.

Baseline and longitudinal changes in biomarkers reflecting PC-ILD evolution, including circulating factors and cell-types from detailed serological and cellular analysis, will be assessed in multilevel models for repeated measures to test associations according to the presence or absence of PC-ILD at late time points (10-15 months), and according to progression, resolution, or persistence of radiological patterns over follow up time points.

Analyses will be performed using standard epidemiological and statistical genetics methodology. This will include cross-sectional and longitudinal studies, and analyses of disease prevalence and incidence.

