Analysis design and choice of controls will be dependent upon the precise nature of the research question. Identification of risk factors for a specific COVID-19 sequela would involve controls both from within UKILD-Long COVID (without the sequela) and serology-positive controls with prospective questionnaire and healthcare record linkage from Longitudinal Population Studies (for example, UK Biobank, Coronagenes, EXCEED) and pre-existing disease cohorts. Analyses aiming to characterise and understand the clinical features, subtypes and trajectories of sequelae (for example, sarcopaenia) would evaluate the cross-sectional and longitudinal clinical data and biomarkers of UKILD-Long COVID participants who are presenting with the sequelae being studied.

The participant organisations making up the UKILD-long COVID study group have extensive experience of development of, and collaborative use of, disease-specific and general population cohort studies both nationally and internationally enabling access to control populations and alignment of research strategies for rapid validation and replication of findings.

Statistical significance thresholds will be defined in advance of each analysis and will take into account issues of multiple testing and *a priori* evidence.

Data and all appropriate documentation will be stored for a minimum of 10 years after the completion of the study, including the follow-up period.

Project statistician: [name] email:

[contact]
National Heart and Lung Institute
[name]
[name]

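### The 6-month symptom, quality-of-life and exercise summaries will come from people who opted in to an optional visit, and Section 7.0 plans only a descriptive analysis for them

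*Combined protocol and SAP*

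**What the plan says.** **Schedule.** In the Section 3.1 table, the secondary outcomes for breathlessness, fatigue, cognition, quality of life and exercise capacity carry the time points "3 month, 6 months (+/- 6 weeks) and 12 months (+/- 3 months) post SARS-CoV-2 infection".

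**Visits.** Section 3.2.1 states "Visit 2 is optional" and "Visits 1 and 3 are obligatory". Section 5.1 repeats this, but also says that "Tier 2 participants may also agree to a final follow up assessment and an optional interim assessment", which reads as if the final visit were voluntary too.

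**Collection.** Section 3.2 has Tier 2 participants complete the questionnaires "at the end of each study visit". Someone who skips Visit 2 therefore has no 6-month study score. The same section requires no study investigations for people co-enrolled in PHOSP-COVID.

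**Analysis.** Section 7.0 lists "physiological performance, and patient-reported outcome measures" among the items of a descriptive analysis. Its multilevel repeated-measures models have a different subject: "Baseline and longitudinal changes in biomarkers reflecting PC-ILD evolution". It also mentions, in general terms, "clinical features, subtypes and trajectories of sequelae". It gives no expected Visit 2 attendance, no missing-data method, no population for each time point and no comparison of attenders with non-attenders.

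**The concern.** A descriptive summary at each scheduled time would use all available participants at 3 and 12 months and only the volunteers at 6 months. Whether someone agrees to an extra visit could plausibly depend on how they feel: the more breathless may want to be seen, or may be unable to travel. In either case the 6-month figure would differ from its neighbours partly because of who attended. A reader who sets the three figures side by side could then take selection for early recovery, a plateau or a relapse.

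The 3- and 12-month scores needed to adjust for much of this are already collected, and Section 7.0 already contains a suitable type of model, though for other outcomes.

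**Working it through.** The documents give no SD, effect size, within-person correlation or expected Visit 2 uptake, so there is no planned figure to reproduce. Every number in steps 1 to 3 is an assumption or follows from one.

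**Step 1: the identity.** Let p be the share attending Visit 2 and d the attender-minus-non-attender difference in the 6-month score. The mean over everyone is p × (attender mean) + (1 − p) × (non-attender mean). Hence

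bias of the attenders' mean = (1 − p) × d.

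In SD units:

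| d | p = 30% | p = 50% | p = 70% | p = 90% |
|---|---|---|---|---|
| 0 | 0 | 0 | 0 | 0 |
| 0.2 | 0.14 | 0.10 | 0.06 | 0.02 |
| 0.5 | 0.35 | 0.25 | 0.15 | 0.05 |

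**Step 2: on a score scale.** Assume a score where higher is worse, with true means 12, 10 and 7 at 3, 6 and 12 months. Assume between-person SD 7 and visit SD 3, so total variance is 49 + 9 = 58 and within-person correlation is 49/58 = 0.845. Uptake is 50%, and the log-odds of attending change by 0.05 or 0.10 per point of the 3-month score (odds ratios per 10 points of e^0.5 = 1.6 and e^1.0 = 2.7).

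In simulation, attenders then differ from non-attenders at 3 months by 2.79 or 5.13 points. With equal variances, d at 6 months is the correlation times that difference, so the bias is 0.5 × correlation × difference. The total variance is held at 58 while the correlation varies:

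| Correlation | Slope 0.05: bias | Attenders' 6-month mean, sicker / fitter attend | Slope 0.10: bias | Attenders' 6-month mean, sicker / fitter attend |
|---|---|---|---|---|
| 0.50 | 0.70 | 10.7 / 9.3 | 1.28 | 11.3 / 8.7 |
| 0.60 | 0.84 | 10.8 / 9.2 | 1.54 | 11.5 / 8.5 |
| 0.845 | 1.18 | 11.2 / 8.8 | 2.17 | 12.2 / 7.8 |

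Direct simulation agrees with these means. The true value is 10.0 throughout. Only the cell with the steeper slope, the highest correlation and sicker people attending exceeds the 3-month mean of 12.

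**Step 3: does a repeated-measures estimate help?** This is a separate simulation (n = 400,000) with higher scores better, true means 0, 0.30 and 0.50 SD, correlation 0.6, and sicker people more likely to attend (log-odds 0.7 per SD). The model-based figure uses everyone's 3- and 12-month scores. Results are 6-month means, true value 0.30:

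| Attendance depends on | Estimate | 30% attend | 50% | 70% | 90% |
|---|---|---|---|---|---|
| Nothing | Attenders only | 0.30 | 0.30 | 0.30 | 0.30 |
| 3-month score | Attenders only | 0.03 | 0.11 | 0.19 | 0.26 |
| 3-month score | Model-based | 0.30 | 0.30 | 0.30 | 0.30 |
| 6-month score itself | Attenders only | −0.14 | −0.01 | 0.11 | 0.23 |
| 6-month score itself | Model-based | 0.05 | 0.12 | 0.19 | 0.26 |

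Attendance that depends on the average of the 3- and 12-month scores gives almost the same result as the 3-month case (0.03, 0.11, 0.18, 0.26), and the model again returns 0.30. The model removes the bias when uptake depends on observed scores, and only part of it when uptake depends on the unobserved one.

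**Step 4: why following the same attenders is not enough.** With 50% uptake depending on the 3-month score, the attenders' means at 3 and 6 months are −0.31 and 0.11. Their change is 0.42 SD against a true 0.30, because people selected for a low 3-month score regress towards the mean.

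**The case against.** The strongest reply is that the plan specifies no trend or recovery curve for these scores. The descriptive sentence in Section 7.0 gives no time points; those come from the Section 3.1 table. Section 7.0 also allows longitudinal analyses in general terms and leaves the design to the research question. A reader might infer that the plan commits to a distorted recovery curve, and the documents do not support that. What remains is a gap: outcomes scheduled at three times, the middle one voluntary, with no stated handling. The general wording names neither an outcome nor a method for missed visits, so it does not fill the gap.

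A reader might also infer from the most extreme illustration that a true improvement would appear as a worsening. That needs both the steeper slope and a correlation of about 0.84. At 0.5 to 0.6 the attenders' mean is 11.3 to 11.5, still below 12. The steeper slope itself makes attenders about 5.1 points worse than non-attenders at 3 months, more than twice the 2-point change in question.

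Three limits on scope also stand. These are secondary outcomes, and the primary radiological endpoint is not affected. With Visits 1 and 3 obligatory, the optional visit does not touch the 3-to-12-month comparison. PHOSP-COVID co-enrolled participants may have 6-month data under a visit pattern set outside this document.

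**Conclusion.** The point holds as a risk left open by the plan. For participants scored at study visits, a descriptive 6-month summary covers only those who opted in. It is not comparable with the 3- and 12-month summaries if uptake is related to the score.

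Neither the size nor the direction of any bias can be derived from the documents. Under the assumptions in step 2, the attenders' 6-month mean lies between about 7.8 and 12.2 against a true 10.0, an error of 0.7 to 2.2 points either way; it is zero if uptake is unrelated to the score. For scale, the assumed 3-to-6-month change is 2 points.

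The change should be made: the remedy uses data already collected and a type of model already in the plan. The statement that the 3-to-12-month contrast is safe from this problem rests on Visit 3 being obligatory, which Section 5.1 leaves unclear.

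**What to change.** In Section 7.0:

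1. Estimate the patient-reported and physiological outcomes with the multilevel repeated-measures model already planned for biomarkers, fitted to all participants with all their available visits. Report model-based means at 3, 6 and 12 months.
2. Make the 3-to-12-month change the main contrast.
3. Show raw 6-month means only beside the 3- and 12-month means of the same attenders, as a display and not as the estimate (step 4).
4. Tabulate the number and 3-month characteristics of Visit 2 attenders and non-attenders.
5. Add a simple sensitivity analysis for attendance that depends on the 6-month score, for example shifting the unobserved 6-month scores by a range of amounts fixed in advance.
6. State where the 6-month scores of PHOSP-COVID co-enrolled participants come from.

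Separately, reconcile the wording on the final visit in Section 5.1 with the statement that Visits 1 and 3 are obligatory.

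The cost is a little more analysis, with no new visit or data. The model relies on scores being missing at random given those observed and corrects only partly if that fails, which is why item 5 is needed.

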8.0 REGULATORY ISSUES

8.1 Ethics approval

The Study Coordination Centre has obtained approval from the Riverside Research Ethics Committee (REC) and Health Regulator Authority (HRA). The study must also receive confirmation of capacity and capability from each participating NHS Trust before accepting participants into the study or any research activity is carried out. The study will be conducted in accordance with the recommendations for physicians involved in research on human subjects adopted by the 18th World Medical Assembly, Helsinki 1964 and later revisions.

8.2 Consent

Consent to enter the study must be sought from each participant only after a full explanation has been given, an information leaflet offered and time allowed for consideration. Signed participant consent should be obtained. The right of the participant to refuse to participate without giving reasons must be respected. After the participant has entered the study the clinician remains free to give alternative treatment to that specified in the protocol at any stage if he/she feels it is in the participant's best interest, but the reasons for doing so should be recorded. In these cases the participants remain within the study for the purposes of follow-up and data analysis. All participants are free to withdraw at any time from the protocol treatment without giving reasons and without prejudicing further treatment. Participants who opt for Tier 1 can be consented by phone and provide a signed consent form by post/email.

8.3 Confidentiality

The Chief Investigator will preserve the confidentiality of participants taking part in the study and is registered under the Data Protection Act. Data and all appropriate documentation will be stored for a minimum of 10 years after the completion of the study, including the follow-up period which falls within the defined end date.

8.4 Indemnity

Imperial College London holds negligent harm insurance policies which apply to this study.

8.5 Sponsor

Imperial College London will act as the main sponsor for this study. Delegated responsibilities will be assigned to the NHS trusts taking part in this study.

8.6 Funding

This study is funded by a research grant award from UKRI MRC Ref MR/W006111/1. Individual researchers will not receive any personal payments or any other benefits for taking part in this research.

8.7 Audits

The study may be subject to inspection and audit by Imperial College London under their remit as sponsor and other regulatory bodies to ensure adherence to GCP and the UK Policy Frame Work for Health and Social Care Research.

9.0 STUDY MANAGEMENT

[name], Chief Investigator and has overall responsibility for the management of the study, the day-to-day management of the study will be co-ordinated through Imperial College National Heart and Lung Institute.

10.0 PUBLICATION POLICY

Final results of the study will be disseminated in the form of a manuscript/s in a peer-reviewed journal scientific journals, presented at national and international conferences and in local meetings. In addition, where relevant, data from potential interim analyses will be presented at (a) relevant congress (es). In addition, the study database will be made available for future research.

